Level of harm resulting from self-harm incidents: Following Hawton et al [1], the level of harm resulting from self-harm incidents will be measured as follows: incidents will be classified as resulting in a high level of harm when they involve loss of life, resuscitation in prison, an overnight stay in hospital, external hospitalisation on life support or a combination of these. A medium level of harm will be defined as external hospitalisation other than life support (NOT an overnight stay) and a low level of harm will be defined as any episode not needing resuscitation or external hospitalisation. The level of harm will be recorded by the individual on the self-harm incidents' log (participants), for non-fatal incidents, and cross referenced with data recorded in the self-harm incidents logs (prison and SystmOne). Any deaths will be reported in the self-harm incidents logs (prison and SystmOne). For each participant, we shall calculate an average level of harm across all incidents.

Self-harm thoughts: Self-harm thoughts will be measured in a weekly diary on a Likert Scale. Women will be asked to report how often they have had thoughts of self-harm since the due date for their last weekly diary (not at all; almost never; sometimes; almost always; all the time).

Objectives	Outcome Measures	Timepoint(s) of evaluation of this outcome measure (if applicable)
Primary Objective To compare the effect of modified PIT versus TAU on incidents of self-harm	Self-harm incidents (composite of self-report and prison/healthcare records)	8-week post baseline (primary outcome); 12-weeks post baseline
Secondary/Exploratory Objectives To compare the effects of PIT versus TAU on key psychological measures: suicidal ideation, depression, hopelessness, self-esteem and wellbeing, on the level of harm resulting from self-harm incidents, on the frequency of self-harm thoughts, and on the participant's ACCT status.	Becks Scale for Suicide Ideation Becks Depression Inventory Beck Hopelessness Scale Rosenberg Self-Esteem Scale Warwick-Edinburgh Mental Well-Being Scale Prison ACCT documents Self-reported self-harm thoughts Likert scale (in the diary) Self-reported level of harm resulting from self-harm incidents cross referenced with prison records and SystmOne	8-weeks post baseline; 12- weeks post baseline
Process Evaluation	Therapy Satisfaction Questionnaire	10 weeks post baseline

Table of outcomes.

TRIAL DESIGN

Pragmatic randomised controlled trial

	IRAS No: 241606	

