During the study period (12-weeks), all participants will complete a weekly diary and the Self-Harm Incidents' Log (Participants), alone, with a trusted peer, or with the research assistant. They will also complete the Concomitant Therapies Form with a research assistant. The diary will include any thoughts of self-harm that have occurred since the last diary date, and any life events which have influenced their self-harm (including the time spent outside their cell). The Self-Harm Incidents' Log (Participants) will include incidents of self-harm in the last week and the severity of the incidents of self-harm. The Concomitant Therapies Form will contain information on any new therapy that has been started during the study period. Information in the Self-Harm Incidents' Log (Participants), will be cross checked with information from prison records (e.g. self-harm incidents databases) and SystmOne using the relevant Self-Harm Incidents' Logs. Concomitant Medications will be recorded from SystmOne on the concomitant therapies this information will be checked using the relevant details for the concomitant therapies this information will be checked using the relevant prison or healthcare databases. We shall also collect the dates and duration of time that women spent on a basic regime during the intervention period from NOMIS on the Basic Regime Data Collection Form.

At 8-weeks and 12-weeks, all participants will complete the secondary outcome measures (BSS; BDI-II; BHS; RSE; WEMWBS) and the health related quality of life scales (EQ-5D-5L; SF-12) and we shall record on the ACCT Status Form whether or not they are participating in the ACCT process.

If a participant is transferred part way through the research, we will seek permission from the receiving prison to complete the ongoing measures (e.g. concomitant medication) and the follow up measures. This will require local access to prison and healthcare databases. We will seek permission from the

WORSHIP III	IRAS No: 241606

participant in the consent process to contact their probation office / CRC for help to locate the women to try to complete ongoing and follow up measures.

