Where a participant is able to consent but later becomes incapacitated, the participant will be suspended from the study. If their capacity returns they will be given the opportunity to re-enter the study. When a participant is formally withdrawn from the study, by their own choice or due to ongoing incapacity, identifiable data already collected with consent will be retained and used in the study, if they consented to retention at baseline. No further data will be collected, or any other research procedures carried out, on or in relation to the participant.

Randomisation

WORSHIP III	IRAS No: 241606

Kings Clinical Trials Unit will build a randomisation system. Randomisation will be at the individual level by block randomisation with randomly varying block sizes, stratified by prison. The trial manager/RAs will access the randomisation system, randomise the participants and receive randomisation alerts and will inform the other researchers and the therapists of the allocation for each participant.

Blinding

Blinding of trial participants and care providers is not possible due to obvious differences between the interventions. It is not practical for the research assistants/research associate to be blind as they will need to coordinate the delivery of the therapy in their study prisons. The outcome assessors who collect the post intervention data (8-weeks) and follow-up data (12-weeks) will be blind to the intervention groups. Outcome assessors will include trained Research Nurses/CSOs/volunteers/peer mentors/ students. These outcome assessors will be security trained so they can enter the prison independently to complete their assessments and will have no other involvement in the research. The trial manager will ensure that outcome assessment takes place at a time and in a location of the prison which will avoid the assessors interacting with the RAs and therapists in a way that could reveal any participant's allocation. If a participant is transferred to a remote site which cannot be accessed by the outcome assessors, they will be followed up by a research assistant who is unaware of their randomisation status. E.g. the RA from London will follow up the RA from Manchester's participants.

Emergency Unblinding

Emergency unblinding should not be necessary as the investigators and therapists will not be blinded and will be able to respond to any serious adverse events in accordance with the protocol.

Baseline data

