The following baseline data will be collected in a 1-hour interview with a research assistant/associate/research nurse/CSO:

- The Eligibility Form will be competed to double check that participants fit the inclusion/exclusion criteria
- The bespoke WORSHIP III Demographic and Personal History Questionnaire designed to collect baseline variables which may have an effect on the participant's self-harm, such as separation from children.
- The Prison Screening Questionnaire (PriSnQuest) [34] is a questionnaire developed to screen for possible serious mental illness within a criminal justice setting.
- The bespoke Mental Health History Form (Self Report) is designed to record people's mental health diagnoses and history, including previous contact with services, their past medication use, details about their most recent episode of self-harm, and previous support they have received for their self-harm (cross referenced with SystmOne).
- The bespoke Alcohol and Drug History Form (Self Report) designed to capture the participant's history of drug and alcohol use and any past treatment (cross referenced with SystmOne).
- The bespoke Self-Harm History Questionnaire details the types of self-harm women have used in the past, whether they have used these types of self-harm in prison, whether they have used

WORSHIP III	IRAS No: 241606

the types of self-harm in the last year and the frequency of each type of self-harm in the last year.

- MacLean Screening Instrument for Borderline Personality Disorder (MSI-BPD) [35], a questionnaire which assesses whether the person is displaying signs of BPD; a common diagnosis in women prisoners who self-harm [4].
- All secondary outcome measures (BSS; BDI-II; BHS; RSE; WEMWBS)
- The health economics measures (EQ-5D-5L; SF-12).

Trial assessments

- Participants will be asked to complete a weekly diary which assesses self-harm thoughts and life events which may affect people's self-harm, including the amount of time that the participant has spent outside their cell. The diary will be self-completed by the participant, with a peer mentor or completed with a research assistant.

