- Participants will be asked to complete a weekly Self-Harm Incidents' Log (Participants) which will record acts of self-harm and the severity of these acts. The log will be self-completed by the participant, with a peer mentor or completed with a research assistant. This will be cross referenced with prison and healthcare records using the Self-Harm Incidents' Logs (prison and SystmOne).
- Participants will be asked to complete a weekly Concomitant therapies form. The forms will be completed with a research assistant. This will be cross referenced with prison and healthcare records, if necessary.
- The research assistant will complete the Concomitant Medications Log on a weekly basis using SystmOne.
- Post intervention assessments at 8-weeks will be collected during a 1-hour interview with a blinded outcome assessor and will include all secondary outcome measures (BSS; BDI-II; BHS; RSE; WEMWBS) and the health related quality of life measures (EQ-5D-5L; SF-12).
- The participant's ACCT status will be recorded by the research assistant.
- Participants randomised to receive PIT will be asked to complete the Therapy Satisfaction Questionnaire at 10 weeks with an unblinded member of the research team.
- We shall also collect from NOMIS the amount of time that each participant spent on a basic regime from baseline to 8 weeks.

Long term follow-up assessments

• Participants will be asked to complete a weekly diary which assesses self-harm thoughts and life events which may affect people's self-harm, including the amount of time that the participant has spent outside their cell. The diary will be self-completed by the participant, with a peer mentor or completed with a research assistant.

	IRAS No: 241606
WORSHIP III	

- Participants will be asked to complete a weekly self-harm incidents' log (participants) which will record acts of self-harm and the severity of these acts. The log will be self-completed by the participant, with a peer mentor or completed with a research assistant. This will be cross referenced with prison and healthcare records.
- Participants will be asked to complete a weekly Concomitant Therapies Form. The forms will be completed with a research assistant. This will be cross referenced with prison and healthcare records, if necessary.
- The research assistant will complete the Concomitant Medications Log on a weekly basis using SystmOne.

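### Self-harm thoughts are rated only in a diary that an unblinded research assistant may complete with the woman; adding the item to the two blind interviews would avoid this cheaply

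*Protocol*

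**What the plan says.** Frequency of self-harm thoughts appears in the Secondary row of the Trial Summary and, in the body, under Exploratory outcomes. The latter section gives its source: "Self-harm thoughts will be measured in a weekly diary on a Likert Scale". The table of outcomes repeats it as "Self-reported self-harm thoughts Likert scale (in the diary" and gives the timepoints of its row as "8-weeks post baseline; 12- weeks post baseline".

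On who fills in the diary, Trial assessments says: "The diary will be self-completed by the participant, with a peer mentor or completed with a research assistant". Trial procedures gives the same routes for the whole 12-week study period: "all participants will complete a weekly diary and the Self-Harm Incidents' Log (Participants), alone, with a trusted peer, or with the research assistant".

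The Blinding section says of research assistants: "It is not practical for the research assistants/research associate to be blind as they will need to coordinate the delivery of the therapy". Of the follow-up data it says: "The outcome assessors who collect the post intervention data (8-weeks) and follow-up data (12-weeks) will be blind to the intervention groups".

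The blind interviews, set out under Trial assessments (8 weeks) and Long term follow-up assessments (12 weeks), "will include all secondary outcome measures (BSS; BDI-II; BHS; RSE; WEMWBS"), together with EQ-5D-5L and SF-12. Self-harm thoughts are not in that list.

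**The concern.** The five psychological scales and the self-harm thoughts item are all self-reports compared between arms at the same two timepoints. The scales are taken by someone who does not know the allocation. The thoughts item, when a woman needs help with her diary, may be given to the person who arranges therapy in her prison. A woman who has received PIT may report fewer thoughts to that person than she would to a stranger, and a control woman has no matching reason to do so.

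The item matters more than its exploratory heading suggests. The Rationale proposes that PIT works by reducing self-harm thoughts, which then leads to fewer incidents. A difference on this item would be read as support for that pathway. The protocol also makes it easy to assume that the item is collected blind, because the Trial Summary calls it secondary and the blind interviews are said to contain all the secondary measures.

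**Working it through.** The protocol gives no figure for this point, so the check is a comparison of its sections.

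1. **Is it a between-arm outcome at 8 and 12 weeks?** Yes. It is in the Secondary row of the Trial Summary, in the secondary/exploratory objective, and in the table of outcomes with both timepoints.
2. **Is there any source other than the diary?** No. Level of harm, in the same table row, is cross-referenced with prison records and SystmOne. Self-harm thoughts have no second source.
3. **Can an unblinded person help complete it?** Yes. The research assistant is one of three routes, and the Blinding section says research assistants cannot be blind. The one exception there is for participants transferred to a remote site, who may be followed up by an assistant unaware of their allocation. It is not extended to the weekly diary in general.
4. **Is the item in the blind interviews?** No. Both lists contain BSS, BDI-II, BHS, RSE, WEMWBS, EQ-5D-5L and SF-12. The diary is a separate bullet, and ACCT status is another, assigned to the research assistant.
5. **Does the protocol say that the diary is masked?** No. The sentence under Blinding concerns the outcome assessors and the data they collect, and the two assessment sections define those data by naming the scales.
6. **Does it say that the diary is not masked?** Not directly. For the Therapy Satisfaction Questionnaire it says that an unblinded team member will be present. For the diary, the reader has to combine the list of completion routes with the Blinding section.
7. **How often would help be given?** Not stated. The protocol expects low literacy among the women (Primary outcome, Consent), so some assisted completion is likely, but no proportion can be derived.

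Steps 1 to 4 establish the gap. Steps 5 and 6 show that it lies in coverage and clarity and is not a contradiction. Step 7 leaves its size open.

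**The case against.** The strongest reply is that nothing promised has been withheld. The Blinding section describes what outcome assessors collect, the assessment sections say exactly what that is, and the diary and ACCT status are openly listed apart. This stands. A reader might infer that the protocol promises masking for every 8- and 12-week outcome and then breaks that promise; the wording does not go so far.

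A reader might also infer that the diary loses more data than the interviews, because interviews are offered to released women. The documents do not support that. Trial procedures says that both ongoing and follow-up measures will be pursued after transfer or release.

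A third tempting step is to put a number on the bias. Assume an item SD of 1.0 to 1.2, 105 women per arm, no true effect and a two-sided 5% test. The standard error is SD × √(2/105), or 0.138 to 0.166. With a spurious shift d, the false-positive rate is Φ(d/SE − 1.96) + Φ(−d/SE − 1.96). A shift of 0.1 category gives about 9% to 11%, and 0.2 gives about 23% to 31%. The arithmetic is right, but neither the SD nor the shift comes from the protocol. It shows what a bias of that size would do, not that one exists.

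Other points carry weight. The body heads the outcome exploratory. The women know their allocation, so a blind assessor cannot remove expectancy or gratitude. The completion routes are the same in both arms, and diaries completed alone are unaffected. BSS, a related construct, is collected blind, and the mediators named as examples in the Statistical analysis plan section (hopelessness, self-esteem) are too. A weekly item also belongs naturally in a weekly diary. These points lower the priority, but they do not explain why the item should be left out of interviews that take place anyway.

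**Conclusion.** The point holds as a cheap improvement to an outcome headed exploratory. Self-harm thoughts at 8 and 12 weeks rest on a single self-report item with no cross-check, which an unblinded research assistant may complete with the woman. The blind interviews omit it while being described as complete for the secondary measures. This leaves an avoidable interviewer effect, confined to assisted diaries, on the hypothesised mechanism.

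The direction and size of any bias are unknown. They depend on the share of assisted diaries, whether that share differs between arms, and how far a woman's answer changes with the listener; the protocol gives none of these. The primary outcome and the five psychological scales do not depend on this item.

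**What to change.** - Add the same five-point self-harm thoughts item, with a past-week recall, to the blind assessor's interviews at 8 weeks (Trial assessments) and 12 weeks (Long term follow-up assessments). Use those answers for the between-arm comparison at these timepoints.
- Keep the weekly diary series as an analysed supporting measure. Record for each diary whether it was completed alone, with a peer or with a research assistant, and report this by arm.
- In the Blinding section, name the outcomes collected blind, and state that the diary, the participant incidents log and ACCT status are not.

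The cost is one extra case report form item at two interviews that already take place, a completion-mode field on the diary, and a short amendment, with no extra visits or staff. There are two downsides. The construct gains a second recall definition, because the diary asks about the time since the last diary was due. Blind collection also leaves in place any reporting bias that comes from women knowing their allocation.

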• To compare the effects of PIT versus TAU on key psychological measures: suicidal ideation, depression, hopelessness, self-esteem and wellbeing, on the level of harm resulting from self-harm incidents, on the frequency of self-harm thoughts, and on the participant's ACCT status at 8 weeks.

Outcome measures

Primary outcome

	IRAS No: 241606	
WORSHIP III		

The primary outcome is the total number of self-harm incidents in the 8-week period from baseline. We shall also be measuring the total number of self-harm incidents in the 12-weeks from baseline. All self-harm which takes place at a specific time point will count as one incident. For example, if someone cuts themselves on their neck and arm at the same time this will count as one incident; however, if they cut themselves at two different times, in the same day, this will count as two incidents e.g. when there is a gap of 30 minutes between incidents. This approach is consistent with the way incidents of self-harm are recorded on SystmOne and the prison self-harm records e.g. the self-harm incidents log/ACCT/NOMIS/F213.

The primary outcome will be a composite of self-harm incidents derived from self-report, medical databases (SystmOne) and prison databases or paper records (NOMIS; F213 forms, ACCT folders, self-harm incidents logs; daily officer's logs) checked for double entry. This approach was recommended in Borschmann et al (2017) who conclude that relying on one data source for self-harm incidents in incarcerated adults could substantially under-ascertain the actual number of events [23]. Self-harm acts will be recorded on the self-harm incidents logs (participants, prison and SystmOne) and then checked for double entry before they are entered into the CTU database. The date and time of each self-reported incident will be recorded to allow cross-checking with medical and prison records, which record self-harm incidents by date and time, to check for duplication.

Both the intervention group and the control group will be asked to complete a weekly self-harm incidents' log (participants) outlining the number of times they have self-harmed since the last entry. All participants (in control and intervention arm) will be able to self-complete the log, at the end of one week, or complete the log with a research assistant. We will explore with each prison recruiting trusted peers to assist with log completion if the women have low literacy.

Secondary outcomes

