Publicity posters and leaflets will also be posted around each prison and adverts will be placed in prison newsletters/papers. We shall also explore with each prison whether it is possible for leaflets to be sent to all prisoners' cells including people who are on the segregation unit to ensure that everyone has an equal chance of participation. The research will be advertised on prison radio and at recruitment events in the prison. We shall approach Samaritan Listeners and women prisoners who work in Safer Custody for their help advertising the research to their peers. We shall also visit different locations in the prison to speak directly to staff and run coffee mornings/lunchtime 'meet and greets' to raise awareness of the research. All advertising will detail how the women can contact the research team to see if they are eligible to participate in the research. This method of recruitment will be used in addition to screening since prison records may not capture all people who have self-harmed in the last month due to some women hiding their self-harm from staff.

Staff Participants

We shall visit different locations in the prison to speak directly to staff, so they are familiar with the research and will run Coffee Mornings/Lunchtime 'meet and greets' to raise awareness of the research. Adverts and posters will be placed in areas of the prison that staff frequent with contact details, so they can hear more about the project. We will also send a global email to all staff advertising the research. We shall attend full staff briefings or other staff meetings and present the research to staff. Staff for the focus groups will be approached directly by members of the research team regarding participation. This may include face-to-face contact or emails.

Payment

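### The participants' self-harm log, one source of the primary count, is given two different recall windows, and one of them leaves gaps after a late or missed log

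*Protocol*

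**What the plan says.** The primary outcome is a count over a fixed period: "The primary outcome is the total number of self-harm incidents in the 8-week period from baseline". It is assembled from several sources: "The primary outcome will be a composite of self-harm incidents derived from self-report, medical databases (SystmOne) and prison databases or paper records". The self-report source is the Self-Harm Incidents' Log (Participants), and the Protocol describes its coverage in three ways.

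- Outcome measures, Primary outcome: the weekly log is completed "outlining the number of times they have self-harmed since the last entry".
- Trial Procedures: the log "will include incidents of self-harm in the last week and the severity of the incidents of self-harm".
- Trial assessments: the log is a weekly form that takes in each act and how severe it was. This fixes the frequency but no recall window. The long-term follow-up list does the same.

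The companion diary, which feeds only an exploratory outcome, has a window that reaches back to the previous diary. Trial Procedures says: "The diary will include any thoughts of self-harm that have occurred since the last diary date". The Exploratory outcomes section asks "how often they have had thoughts of self-harm since the due date for their last weekly diary".

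On why self-report matters, the Recruitment section notes that "prison records may not capture all people who have self-harmed in the last month due to some women hiding their self-harm from staff".

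**The concern.** A count over 8 weeks is only as complete as the days its sources cover. Self-report is in the composite because a single source can miss many events, and it is the source best placed to catch self-harm that staff do not see. If staff follow the Trial Procedures wording, a woman who returns a log after a gap is asked about the most recent seven days only. The earlier days of the gap then drop out of the self-report source. This is fixed when the data are collected: an incident that was never asked about cannot be restored in the analysis. The database may show that a form was missed, but unless each log carries the dates it covers, nobody can tell whether the next form closed the gap.

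The Sample size section also gives weekly self-report as one of two reasons for expecting little attrition in the primary outcome, so the plan relies on this source being continuous.

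**Working it through.** The Protocol gives no figure to reproduce on this point. The check compares the two windows and then illustrates the scale.

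**1. Days covered under each wording.** Count days from baseline; the primary window is 8 × 7 = 56 days. Suppose the last completed log was on day 14.

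| Next completed log | Back to last entry | Last seven days | Uncovered by the second |
|---|---|---|---|
| Day 21, on schedule | 15–21 | 15–21 | none |
| Day 24, three days late | 15–24 | 18–24 | 15–17 (3 days, 3/56 = 5.4%) |
| Day 28, day 21 log missed | 15–28 | 22–28 | 15–21 (7 days, 7/56 = 12.5%) |
| None afterwards | nothing after 14 | nothing after 14 | no difference |

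The wordings differ only when a log is late, or is missed and then followed by a completed one. A woman who stops logging is lost to self-report under both. Logs run to 12 weeks, so a missed week-8 log followed by a week-9 log would be recovered under the Primary outcome wording. Each self-reported incident carries a date and time, so it can be placed inside or outside the 8-week window. A log completed early would cover some days twice under the fixed-week wording, but the date and time matching should limit duplicates.

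**2. What is lost from the composite.** Incidents on uncovered days that stand in SystmOne or prison records are still counted. Let *s* be the share of incidents known only from self-report and *k* the number of uncovered weeks. Then

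share of the 8-week count lost = (*k*/8) × *s*.

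The Protocol does not give *s*; 0.10 to 0.50 is assumed. For scale, the Protocol's control mean of 6.65 over 8 weeks is 6.65/8 = 0.83 per week. That mean comes from prison data, so it serves as a yardstick only.

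| | *s* = 0.10 | *s* = 0.25 | *s* = 0.50 |
|---|---|---|---|
| *k* = 1 | 0.08 (1.25%) | 0.21 (3.1%) | 0.42 (6.25%) |
| *k* = 2 | 0.17 (2.5%) | 0.42 (6.25%) | 0.83 (12.5%) |

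All incidents of a missed week would be lost only if *s* = 1, that is, if records held none of them.

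**3. Rate ratio.** With *k* uncovered weeks on average in each arm,

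observed ratio = true ratio × (1 − *s* × *k*_PIT/8) / (1 − *s* × *k*_TAU/8).

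If *k* is the same in both arms and *s* is common, the factor is 1. The sign otherwise depends on which arm has more gaps. Take a ratio of 0.67 (the 33% reduction the trial is sized for), *s* = 0.25, and two uncovered weeks in one arm only:

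- gaps in usual treatment only: 0.67/0.9375 = 0.715;
- gaps in PIT only: 0.67 × 0.9375 = 0.628.

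These are extreme cases that show the direction is open. They are not estimates.

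**The case against.** The strongest reply is that this is loose phrasing in a procedural summary. The outcome is defined in the Primary outcome section, which has the gap-free window and requires a date and time for each incident. A weekly form is naturally described as covering a week. The form itself is not shown and may carry a single correct window. All of this is fair, and it limits how far one can say that sites would actually measure different things. It does not remove the contradiction: two current sections describe the same form differently, no other section settles it, and Trial Procedures is a section staff may work from.

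A reader might infer three stronger things that the document does not support.

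- **That every incident in a missed week is lost.** It is not. The composite also draws on SystmOne, NOMIS, F213 forms, ACCT folders and incident and officers' logs. The research assistant monitors self-harm weekly, and risk raised in research or therapy sessions is noted in the records. Only incidents that reach none of these are at risk. The remark about hidden self-harm is made about recruitment, but the behaviour it describes bears equally on outcome records.
- **That a missed log is scored as zero.** No section says so. The Protocol plans missing-at-random analyses and sensitivity analyses, and the detailed handling may be in the SAP. Those methods cannot supply incidents from days that a completed log never asked about.
- **That women receiving PIT log more reliably, so the comparison is biased in a known direction.** Weekly research assistant contact is planned in both arms, through the Concomitant Therapies Form and the weekly health question, and help with the log is offered to all. Randomisation stratified by prison also limits bias from sites reading the wording differently.

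**Conclusion.** The contradiction is real and current, and it concerns a source of the primary outcome. Its consequence is narrow: under the Trial Procedures wording, incidents on days left uncovered by a late log, or by a missed log later followed by a completed one, reach the primary count only if prison or healthcare records hold them. Self-harm hidden from staff on those days would go uncounted.

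For an affected woman, one uncovered week costs about 1% to 6% of her count if 10% to 50% of incidents are known only from self-report. This also assumes incidents fall evenly over the weeks. The trial-wide effect depends further on how many logs are late or missed and then resumed, which the Protocol does not give. Neither the size nor the direction of any effect on the rate ratio can be derived from the document. No sample size or power figure changes.

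**What to change.** - In Trial Procedures, replace the fixed one-week window for the log with: since the last completed log. This matches the Primary outcome section.
- State the same window where the log is listed under Trial assessments and under Long term follow-up assessments.
- Record on the existing form the first and last date each log covers, so that days without self-report in the 8-week window can be identified for each woman.

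The cost is one phrase in each place and two dates on a form already in use. The downside is longer recall after a missed week, with some loss of accuracy in dating incidents. An added catch-up log at 8 weeks is not needed to resolve the contradiction, and someone would have to be named to collect it, since the 8-week interviewer is a blinded assessor.
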